- 6.iii.2.a.1.** Using FLT PET/CT as a measure of cellular proliferation, assess tissue proliferation in disease sites of brain tumor patients before therapy (surgery, chemotherapy or radiotherapy or any combination of these.).
- 6.iii.2.a.2.** Determine level of change in cellular proliferation compared with baseline (Scan 1) in brain tumors at mid-therapy (Scan 2), after completion of therapy (Scan 3) and in the clinical follow-up period (Scan 4), when possible.
- 6.iii.2.a.3.** Correlate levels of cellular proliferation measured by FLT PET/CT at baseline and treatment-induced changes in brain tumor proliferation with clinical response status (clinical categories are complete remission, lesser degrees of response/stable disease, and no response).
- 6.iii.2.a.4.** Assess spatial heterogeneity of FLT uptake to identify local differences in brain tumor disease burden. This aim is a secondary analysis. For patients in which re-operation is clinically indicated, we will mark surgical specimens to co-register with regions of the FLT image. These tissues will be banked for future histological assays.

6.iii.3. BACKGROUND

Cellular proliferation imaging with specific PET agents provides a noninvasive approach to quantify the growth rate of tumors serially and to assess their treatment response. Our research group pioneered the development and validation of [¹⁸F]-fluorothymidine (FLT), which has been shown to accumulate in tissues in proportion to the level of cellular growth (Shields, 1998; Krohn, 2012). During cellular uptake, FLT is transported across the cell membrane and then phosphorylated by *thymidine kinase-1*, resulting in intracellular trapping of the radiolabeled nucleotide (Grierson, 2004). Because of the substitution at the 3'-position, FLT is not a good substrate for *DNA polymerase*. *Thymidine kinase-1* activity is controlled throughout the cell cycle processes, which forms the basis for relating FLT uptake to cellular proliferation. Although FLT is not incorporated into DNA, its retention in cells is directly related to *thymidine kinase-1* activity, which peaks in S-phase and then is destroyed as the cells proceed to division (Weber, 1991; Eriksson, 1994). Our research has shown that uptake is also influenced by blood flow, which led us to develop a simple dynamic PET imaging method to obtain quantitative tissue proliferation rate information separate from tumor blood flow (Muzi

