Figure 6.iii.3 Kinetic model of FLT metabolism is comprised of an exchangeable tissue compartment and a compartment of trapped FLT \ nucleotides. Four rate constants describe kinetic transfer rates between the 2 compartments. FLTMP = FLT-monophosphate; FLTDP = FLT-diphosphate; FLTTP = FLT-triphosphate; FLT-gluc = FLT-glucuronide; Q_e = exchangeable tissue compartment; Q_m = compartment of trapped FLT phosphorylated nucleotides; $C_{p\text{FLT}}$ = concentration of FLT in arterial plasma; C_{met} = concentration of metabolites in arterial plasma. An imaged extraction procedure will be used to recover the arterial input function (O'Sullivan, et al. 2010).

6.iii.10.a.1. Compartmental Analysis

From PET/CT VOI analysis of dynamic data, SUV (30-60 min summed) and parameters reflecting transport (K_1) and FLT flux (K_{FLT}) will be calculated using mathematical modeling analysis as described by Muzi et al (Muzi, 2005a; Muzi, 2005b). The change in these rate parameters between baseline and follow up imaging will also be calculated.

6.iii.10.b. Biologic Correlates

Blood Collection Time Points

Blood samples will be obtained from each participant at the time of dynamic PET imaging. Each blood sample is used both for the determination of radioactivity and metabolite analysis. Blood samples are drawn from patients using a second venous catheter placed in the opposite arm from the injection site or from a clinically placed PICC line or Port-a-cath. Blood samples of 2-3 mL each are collected into heparinized syringes (or a heparinized blood vacutainer) at 15, 30 and 60 minutes after ¹⁸F-FLT injection, which is infused over one minute.

No tissue sampling other than what is required for clinical diagnosis will be done for this study. At the time of resection (or re-resection), tissue not needed for standard clinical care may be labeled with anatomic location co-registered to the PET images and banked for potential future analysis of biomarkers. Any biomarker studies would be described in a separate IRB protocol and would be consented separately from the FLT PET/CT imaging protocol. This consent is already part of the consent for surgery.

6.iii.11. STUDY CALENDAR

Table 6.iii.4

	Pre-Study	Day of [¹⁸ F]FLT baseline	Mid-Rx	Post-therapy Day of [¹⁸ F]FLT (optional)	Post-Rx 1 year or time of suspected recurrence [¹⁸ F]FLT
Confirmed diagnosis of malignant brain tumor	X				
Informed Consent	X				
Demographics	X				
Pregnancy Test **		X		X	X
Vital Signs *	X				

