Abbreviations: RANO, Response Assessment in Neuro-Oncology; CR, complete response; PR, partial response; SD, stable disease; PD, progressive disease; FLAIR, fluid-attenuated inversion recovery; NA, not applicable
* Progression occurs when this criterion is present.
Δ Increase in corticosteroids alone will not be taken into account in determining progression in the absence of persistent clinical deterioration.

The primary analysis variables for the study are:

- Percentage change in K_1 , FLT flux and SUV for [¹⁸F]FLT PET/CT
- Assessment of clinical response per the response criteria listed above.
- Survival

Secondary analysis variables are:

- Heterogeneity in K_1 , FLT flux and SUV for [¹⁸F]FLT PET/CT at baseline.
- Comparison of heterogeneity at different times

6.iii.13. DATA REPORTING / REGULATORY CONSIDERATIONS

Adverse event lists, guidelines, and instructions for AE reporting are described in Section 6.iii.8. The Principal Physician Investigator is responsible for maintaining complete and timely, HIPAA-compliant electronic records of clinical and image datasets.

6.iii.14. STATISTICAL CONSIDERATIONS

6.iii.14.a. Study Description

This is a study involving [¹⁸F]FLT PET/CT imaging of patients with brain tumors at different times during the course of standard treatment. Thirty patients with brain tumors and who are planning standard therapy with surgical resection, chemotherapy or radiotherapy or any combination, will be enrolled. We will evaluate the values for percentage changes in [¹⁸F]FLT PET measures observed following 1-3 weeks of therapy, shortly after finishing therapy and at time of

recurrence or at one year, whichever comes first and explore associations between [¹⁸F]FLT PET parameters and their changes and clinical outcome.

6.iii.14.b. Power Calculations

For hypotheses 2 and 3, we will use patient survival as our outcome variable and the analysis will be based on the Cox proportional hazards model with adjustment for confounding. We have estimated that with 30 patients our study will have power characteristics presented in Table 6.iii.7. These calculations used a value for the study effect of 0.75.

Table 6.iii.7. Power calculation for measuring response	FU=2 yrs	FU=7 yrs
Power without cofounders	0.79	0.80
Power using cofounders, including FDG PET/CT	0.87	0.83
Effect of 15% measurement error	0.89	0.84

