The analysis of data for these hypotheses involves within-subject changes where the variance in values will be less than between-subject FLT results that we have published. Furthermore, this power analysis has assumed that only data from a single volume of interest (VOI) for each subject will be used. In the context of our aims, this could be considered inefficient. In many subjects it will be possible to include data from spatially well-separated and hence substantially uncorrelated sub-regions within large tumors (Spence, 1998) as distinct sampling units for consideration with this hypothesis. Notwithstanding the additional variability that sub-region measurements will have, it is likely that some gains in statistical precision can be realized by this approach. Thus the 90% power estimate is conservative.

Hypothesis 1. Among GBM patients identified as progressing according to Macdonald criteria at 1-month follow-up, the mean FLT flux in true progression cases will be compared to the corresponding mean in the pseudo-progression cases. Preliminary data indicate that 40% of MRI diagnosed progression can be expected to be pseudo-progression. Our data on recurrence vs radionecrosis for KFLT recurrences showed a mean of 0.017 and a standard deviation of 0.005 (Spence, 2006). The mean of the radionecrosis group was 0.004, roughly one-quarter for that for recurrences. Thus, conservatively, assuming that pseudo-progressors showed even a 30% increase over the mean KFLT value, the expected difference between the groups would be 0.017×0.3 or about 0.005. From this, the expected standardized effect is 0.99. Using a 2-sample t-test with significance level of 5% for assessment of the hypothesis, the power of our study is about 95%.

6.iii.14.c. Analysis Plan

Percentage change between pre-treatment and post-therapy measurements will be computed for [¹⁸F]FLT PET/CT measures of transport, K₁, and flux (KFLT). Log transformations will be considered if the rates of change are highly skewed. Outcome analysis studies are directed toward predicting tumor response. In the case of progression, a multivariate logistic regression will be used to produce an analysis of how the combination of standard diagnostics plus the FLT parameters (K₁, KFLT, SUVmean) obtained shortly after therapy can best be combined to

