obtain a prognostic variable for determination of progression. Although the prognostic variable will provide a direct assessment of the probability of response for an individual patient, we will also develop a ROC characterization of its diagnostic performance. We fully appreciate that the small number of patients means that this analysis may suffer from a lack of power but it should be useful in planning a larger follow-up if the results are encouraging.

A similar approach will be used for survival analysis.. Here we will use multivariate Cox regression analysis with both baseline and follow-up variables to be considered.

The heterogeneity of the within-tumor proliferation obtained by application of the elliptical heterogeneity measure developed by Eary et al (2008) will be used in a secondary analysis.

6.iii.14.d. Stratification Factors

Not Applicable.

6.iii.14.e. Reporting and Exclusions

Evaluation of Toxicity: All patients will be evaluable for toxicity from their [¹⁸F]FLT PET.

6.iii.15. LITERATURE CITED

Carlson RW. Sequencing of endocrine therapies in breast cancer--integration of recent data. *Breast Cancer Res Treat* 2002; 75 Suppl 1 S27-32; discussion S33-5.

Carlson RW, Allred DC, Anderson BO, Burstein HJ, Carter WB, Edge SB, Erban JK, Farrar WB, Goldstein LJ, Gradishar WJ, Hayes DF, Hudis CA, Jahanzeb M, Kiel K,

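### The Cox survival analysis does not say which follow-up scans enter or from what time origin; if the scan timed by recurrence (Scan 4) is used as a fixed covariate, its association with survival is biased

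*Combined protocol and SAP*

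**What the plan says.** Section 6.iii.14.b sets the outcome: "For hypotheses 2 and 3, we will use patient survival as our outcome variable", analysed by Cox regression. Section 6.iii.14.c introduces that analysis with "A similar approach will be used for survival analysis" and continues: "Here we will use multivariate Cox regression analysis with both baseline and follow-up variables to be considered".

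The analysis it is said to resemble is the logistic model for progression, which uses FLT parameters "obtained shortly after therapy can best be combined to" give a prognostic variable. Section 6.iii.14.c also defines percentage change only from pre-treatment to post-therapy.

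Section 6.iii.14.a is broader. Besides the changes early in therapy and soon after it ends, it covers the change at a last scan, with this timing and use: "recurrence or at one year, whichever comes first and explore associations between". The associations meant are those of the FLT measures with how patients fare clinically. The study calendar (6.iii.11) labels the last scan "Post-Rx 1 year or time of suspected recurrence". Aim 6.iii.2.a.2 includes change from baseline "in the clinical follow-up period (Scan 4), when possible".

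No section gives a time origin for the Cox model, a landmark, delayed entry, a time-dependent covariate, a rule for patients who die before a scan, or an exclusion of Scan 4.

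**The concern.** The date of Scan 4 depends on the patient's course. A patient scanned at one year has, by construction, lived a year without recurrence. A patient scanned earlier has just recurred. If flux is higher in recurrent tumor, the Scan 4 value separates these two groups, and they differ in survival for reasons that need not involve FLT. A Cox model counting survival from baseline, with that value as an ordinary covariate, credits FLT with the difference.

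At stake is Hypothesis 2 with survival as its outcome. An apparent link could mean only that flux is high once tumor has come back, not that a change in flux predicts what follows. The schema section says promising data will be used to design larger trials, so the error could carry forward.

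**Working it through.** The plan gives no figure on this point. Table 6.iii.7 gives power for the same Cox analysis (0.79 and 0.80 without confounders), but not the event count, significance level or scale of the 0.75 effect. As one reading, 30 events, log hazard ratio 0.75 per SD and two-sided 5% give Φ(√30 × 0.75 − 1.96) = Φ(2.15) = 0.984. The table therefore cannot be reproduced from what is stated. That proves no error and does not bear on this point.

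**Inputs from the documents.** n = 30 (6.iii.14.b). Mean flux is 0.017 in recurrence, with SD 0.005, and 0.004 in radionecrosis (6.iii.14.b). Scan 4 is at the earlier of recurrence and one year (6.iii.14.a).

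**Assumptions not in the documents.** Times to recurrence and from recurrence to death; one year taken as 12 months from the model's time zero; radionecrosis standing in for recurrence-free patients; SD 0.005 applied to both groups; absolute flux used in place of percentage change; every patient has Scan 4.

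**Step 1: the mechanism by hand.** Take exponential times with median 12 months to recurrence and 7 months from recurrence to death. The means are 12/ln 2 = 17.31 and 7/ln 2 = 10.10 months. Half the patients recur before 12 months.
- Scanned at recurrence: mean time to recurrence, given that it comes before 12 months, is 17.31 − 12 × 0.5/0.5 = 5.31 months. Mean survival from baseline is 5.31 + 10.10 = 15.4 months.
- Scanned at one year: 12 + 17.31 + 10.10 = 39.4 months.
- With the clock restarted at Scan 4 the means are 10.10 and 17.31 + 10.10 = 27.4 months. The gap narrows from 24.0 to 17.3 months but does not close.

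The flux means of the two groups differ by (0.017 − 0.004)/0.005 = 2.6 SD, so the Scan 4 value is largely a label for the group.

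**Step 2: simulation under the null.** FLT carries no survival information beyond recurrence status. Each setting had 2,000 runs with a two-sided 5% Wald test. Monte Carlo error is about 1 point near 5% and 2 points near 50%. Cells show the percentage of runs in which the FLT term was significant.

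| Median months to recurrence / recurrence to death | Scan 4 fixed, from baseline (median HR per SD) | Clock from Scan 4 | Clock from Scan 4 plus recurrence status | Scan 3 at fixed time |
|---|---|---|---|---|
| 7 / 7 | 63.2 (1.56) | 32.2 | 6.6 | 5.6 |
| 12 / 7 | 82.9 (1.84) | 62.8 | 7.9 | 5.6 |
| 12 / 12 | 59.3 (1.56) | 40.0 | 8.6 | 6.0 |
| 24 / 12 | 66.0 (1.72) | 55.1 | 8.2 | 5.3 |

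**Step 3: other assumptions.**
- Median recurrence 7, 10 or 14 months and 8 months from recurrence to death (4,000 score-test runs per setting). With follow-up of 24 / 84 months, fixed Scan 4 use gives 59/55%, 78/74% and 86/82%. Restarting the clock alone leaves 26-64%. Stratifying by recurrence as well gives 5.2-6.1%. A repeat over the same 7-14 month range gave 58-87%, 25-64% and 5-6%.
- Weaker separation, 0.010 to 0.014 against 0.017 (1.4 to 0.6 SD), recurrence median 7-10 months: 12-48%.
- Flux depends only on scan date: 36-61% with fixed use, and 18-34% with the clock restarted alone.
- Flux depends on neither date nor recurrence: 5-7%.

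The 6-9% in the adjusted models is probably small-sample behaviour of the Wald test: the adjusted model gives 7-8% even when flux is pure noise.

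**The case against.** The strongest objection is that no sentence puts Scan 4 in the Cox model. Section 6.iii.14.c defines change up to the post-therapy scan, uses parameters from shortly after therapy in the logistic model, and calls the survival analysis similar. The recurrence-or-one-year scan appears in 6.iii.14.a, which speaks of exploring associations and does not mention Cox regression. This stands. A reader might infer that the plan commits to Scan 4 as a survival covariate; the text permits that without stating it. Equally, the Cox sentence widens the covariates to follow-up variables in general, and nothing excludes Scan 4.

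A reader might also infer that every follow-up scan is affected, since each requires survival to the scan. The documents do not support that. Scans 2 and 3 are tied to the treatment schedule, and a fixed-time Scan 3 stays at about nominal error.

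The size is open to challenge too. The event times are assumed, and eligibility covers primary, recurrent and metastatic tumors, so one recurrence process is a simplification. The 0.004 mean is for radionecrosis, and the SD is stated for recurrences only. Scan 4 is done only when possible, so 30 such scans is optimistic. All of this is fair, and is why the result is given as a range.

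Finally, this is a pilot that concedes low power and sets no significance rule for the Cox analysis. That limits the consequences but does not remove the bias in the estimate.

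**Conclusion.** The point holds conditionally. The plan leaves open which follow-up scans enter the survival model, from what time origin, and how recurrence-triggered timing is handled. If Scan 4 is entered as a fixed covariate from baseline, the false-positive rate at nominal 5% is roughly 55-87% under the assumed recurrence medians of 7-14 months, 8 months from recurrence to death, and the proxy flux values. It is about 12-48% with weaker flux separation. The bias needs flux to vary with recurrence or scan date, which the plan's own 0.017 against 0.004 makes plausible; otherwise error stays near nominal. None of these figures is the trial's actual error rate.

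A landmark or reset clock might seem a sufficient cure for Scan 4. It is not: restarting the clock alone leaves about 18-64%, and recurrence status at the scan must be handled as well. For Scans 2 and 3, only the time origin and the restriction to patients who reach the scan need stating.

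**What to change.** In 6.iii.14.c:

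- Name the scan behind the Hypothesis 2 Cox model: the change from baseline to Scan 2 (or Scan 3), with survival counted from the date of that scan among patients alive and scanned. If Scan 2 is chosen, add that change to the section, which now defines only pre-treatment to post-therapy change.
- State that Scan 4 will not enter as a fixed covariate with survival counted from baseline. Report it descriptively, or analyse it with survival counted from the Scan 4 date and stratified by (or adjusted for) whether recurrence triggered the scan. Both parts are needed.
- Report how many patients are left out of each model and why.

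This is wording only, with no added patients or scans. The cost is that patients who die before the landmark scan, or do not have it, drop out of that model. The calendar marks the post-therapy scan optional, so a Scan 3 landmark could also lose living patients; this favours Scan 2. Scan 2 is not guaranteed either, since Section 6.iii.6 lists the mid-therapy scan as possible rather than required. But a patient without the scan has no change value to analyse in any case.
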